5.0 Special Considerations

5.1 Health Insurance Portability and Accountability Act (HIPAA)

It is necessary that PHI be accessed to achieve the goals of this study. All research personnel are trained in HIPAA and routine protections of PHI will apply.

The Informed Consent Form will incorporate wording that complies with relevant data protection and privacy legislation. In accordance with the Health Information Portability and Accountability Act (HIPAA), the written Informed Consent Form must include a subject authorization to release medical information to a regulatory authority, or Institutional Review Board (IRB), to grant access to subject's medical information that includes all hospital records relevant to the study, including subjects' medical history.

The core elements included in the HIPAA authorization are:

- A description of the information to be used or disclosed that identifies the information in a specific and meaningful fashion;
- The name or other specific identification of the person(s), or class of persons, authorized to make the requested use or disclosure;

Protocol Title: ATTAC-19 – Aggrenox To Treat Acute Covid-19 Pro#2020001469

Rutgers, The State University of New Jersey [name]

- The name or other specific identification of the person(s), or class of persons, to whom the covered entity may make the requested use or disclosure;
- A description of each purpose of the requested use or disclosure;
- An expiration date or an expiration event that relates to the individual or the purpose of the use or disclosure;
- Signature of the individual and date.
- 5.2 Family Educational Rights and Privacy Act (FERPA)

N/A

5.3 Code of Federal Regulations Title 45 Part 46 (Vulnerable Populations)

N/A

5.4 General Data Protection Regulation (GDPR)

N/A

5.5 NJ Access to Medical Research Act (Surrogate Consent)

N/A

6.0 Data Management Plan

6.1 Data Analysis

The sample size of 132 patients (66 patients in each arm) was estimated to provide 90% power to detect a relative between-group difference of 20% reduction in composite ordinal scale (from day 0 to day 15) with assumption of mean composite ordinal scale value of 4.5 ± 1.6 (yes) at baseline (day 0) and two-sided P value of 0.05.20 For primary efficacy, we will do an intention-totreat analysis and include all patients who have undergone randomization and will adjust for the minimization variables. We will analyze continuous measures by means of linear regression and present as mean differences. For binary outcomes, we will present data as risk ratios from a binomial regression model.

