1.0 Research Design

1.1 Purpose/Specific Aims

The purpose of this study is to explore the efficacy of Aggrenox (Dipyridamole ER 200mg and Aspirin 25mg), in brand or generic formulation, in patients with SARS-CoV-2 infection with symptoms consistent with COVID-19. For ease, we will identify the drug as Aggrenox, regardless of the formulation.

Among 132 SARS-CoV-2 patients (66 patients in each randomized arm), we will determine the efficacy of Aggrenox on clinical outcomes.

A. Endpoints:

Primary Endpoint:

Change in composite COVID ordinal scale at day 15. Ordinal scale: 1) not hospitalized with resumption of normal activities; 2) not hospitalized, but unable to resume normal activities; 3) hospitalized, not requiring oxygen; 4) hospitalized, requiring oxygen; 5) hospitalized, requiring high-flow oxygen therapy, or noninvasive ventilation; 6) hospitalized, requiring invasive ventilation; 7) ventilation plus additional organ support such as vasopressors, renal replacement therapy and ECMO and 8) death.

Secondary Endpoints:

- 1) all-cause mortality assessed on day 15 and day 28.
- 2) oxygen-free days through day 28.
- 3) invasive-ventilator-free days through day 28.
- 4) ICU-free days through day 28.
- 5) hospital-free days through day 28.
- 6) increase in cycle threshold (Ct) of SARS-CoV-2 PCR test as an approximation of decline in viral load at days 7 and 15.
- 7) decrease in the markers D-dimer/ ferritin/ c-reactive protein at days 7 and 15.
- 8) thromboembolic complications including stroke at day 28.
- 9) Change in COVID ordinal scale at day 28.
- 10) When feasible urine will be analyzed for markers of tubular injury IL-18, kidney injury molecule-1 [KIM-1], neutrophil gelatinase-associated lipocalin [NGAL]), inflammation (monocyte chemoattractant protein-1 [MCP-1]), and repair (human cartilage glycoprotein-40 [YKL-40]

B. Hypotheses / Research Question(s)

Compared to standard care, addition of Aggrenox (Dipyridamole ER 200mg/ Aspirin 25mg), to standard care will result in improvement in composite COVID ordinal scale at day 15. Additionally, combined Aggrenox (Dipyridamole ER 200mg/ Aspirin 25mg orally/enterally), and standard care will reduce need for ventilation, length of mechanical ventilation, hospital length of stay, ICU length of stay and improve survival more than standard care alone in SARS-CoV-2 patients.

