1.2 Research Design and Methods

1: 1 Randomized design.

Arm 1: Aggrenox plus standard care. Participants will receive Aggrenox (Dipyridamole ER 200mg/ Aspirin 25mg orally/enterally), 2 times daily (FDA–recommended dose) starting on the day of enrollment for a total of 2 weeks along with standard care.

Arm 2: Standard care. Participants will receive standard care starting on the day of enrollment for a total of 2 weeks.

We will perform a randomized, 2-arm, open-label single-site pilot study to evaluate the effect of oral Aggrenox (Dipyridamole ER 200mg/ Aspirin 25mg orally/enterally), on clinical outcomes in patients with SARS-CoV-2. In this research proposal, we will randomly assign 132 consenting participants with diagnosis of SARS-CoV-2 to two treatment groups: 1) Aggrenox (Dipyridamole ER 200mg/ Aspirin 25mg orally/enterally) + standard care and 2) standard care alone. Participants will be screened, enrolled, receive treatment and followed for 28 days. The study

Protocol Title: ATTAC-19 – Aggrenox To Treat Acute Covid-19 Pro#2020001469

Rutgers, The State University of New Jersey [name]

aim and procedure will be explained to every eligible subject and informed consent will be obtained from interested subjects or authorized proxy to participate in the study. We do not anticipate problems with enrollment as sufficient number of COVID-19 patients are admitted at Rutgers-NJMS (approximately 2-5 new COVID-19 admissions daily, and total 18-20 patients who are currently admitted at Rutgers-NJMS with 5-6 patients in intensive care units).

Randomization. The P.I. or study coordinator will review the screening and enroll participants in the randomization. Once a participant has been randomized, we will conduct all evaluations irrespective of whether the participant starts the treatment, and how long the participants continues on the treatment or not. SARS-CoV-2 patients will be allocated in a 1:1 randomized fashion using computer generated random sequence to one of two groups: the Aggrenox (Dipyridamole ER 200mg/ Aspirin 25mg orally/enterally), plus standard care or the standard care. Data collection will end after 28 days, or the patient dies or withdraws consent.

A. Research Procedures

Study Procedures:

Day 0 – Screening Visit: (Complete baseline COVID Case report form – Appendix B: Module 1)

- o Review eligibility criteria
- o Obtain informed consent for trial enrollment
- o Demographic data

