Change (as compared to baseline on day 0) in composite COVID ordinal scale at day 15 Ordinal scale: 1) not hospitalized with resumption of normal activities; 2) not hospitalized, but unable to resume normal activities; 3) hospitalized, not requiring oxygen; 4) hospitalized, requiring oxygen; 5) hospitalized, requiring high-flow oxygen therapy, or noninvasive ventilation; 6) hospitalized, requiring invasive ventilation; 7) ventilation plus additional organ support such as vasopressors, renal replacement therapy and ECMO and 8) death.

Secondary endpoints:

- 1) all-cause mortality assessed on day 15 and day 28.
- 2) oxygen-free days through day 28.
- 3) invasive-ventilator-free days through day 28.

Protocol Title: ATTAC-19 – Aggrenox To Treat Acute Covid-19 Pro#2020001469

Rutgers, The State University of New Jersey [name]

- 4) ICU-free days through day 28.
- 5) hospital-free days through day 28.
- 6) increase in cycle threshold (Ct) of SARS-CoV-2 PCR test as an approximation of decline in viral load at days 7 and 15.
- 7) Change in the inflammatory markers D-dimer/ ferritin/ c-reactive protein at days 7 and 15 as compared to baseline on day 0.
- 8) thromboembolic complications including stroke at day 28.
- 9) Change (as compared to baseline on day 0) in COVID ordinal scale at day 28.
- 10) if feasible urine will be analysed for markers of tubular injury IL-18, kidney injury molecule-1 [KIM-1], neutrophil gelatinase-associated lipocalin [NGAL]), inflammation (monocyte chemoattractant protein-1 [MCP-1]), and repair (human cartilage glycoprotein-40 [YKL-40]

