1.5 Sample Size Justification

The sample size of 132 patients (66 patients in each arm) was estimated to provide 90% power to detect a relative between-group difference of 20% reduction in composite ordinal scale (from day 0 to day 15) with assumption of mean composite ordinal scale value of 4.5 ± 1.6 (yes- this is SD) at baseline (day 0) and two-sided P value of $0.05.^{25}$ For primary efficacy, we will do an intention-to-treat analysis and include all patients who have undergone randomization and will adjust for the minimization variables. We will analyze continuous measures by means of linear regression and present as mean differences. For binary outcomes, we will present data as risk ratios from a binomial regression model.

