1.6 Study Variables

A. Independent Variables, Interventions, or Predictor Variables

The following variables will be examined for treatment outcomes of efficacy and/or predict outcomes:

- Treatment
- Baseline temperature
- Baseline SARS-CoV test
- Baseline measure of inflammatory markers

B. Dependent Variables or Outcome Measures

The following variables will be examined for changed as result of treatment or as predictors

- Treatment Compliance
- Change in the fever curve
- Improvement in vital signs
- Time to discharge (if hospitalized)
- Adverse Events (number/percentage/grade)
- Inpatient versus Outpatient
- Change from baseline SARS-CoV test
- Change from baseline inflammatory markers

RUTGERS | eIRB APPROVED

Approval Date:

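### Time to discharge is a listed outcome measure, but the only method that could apply to it is linear regression of means, with no rule for deaths or patients still in hospital at day 28

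*Combined protocol and SAP*

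**What the plan says.** Section 1.6 B (Dependent Variables or Outcome Measures) includes "Time to discharge (if hospitalized" followed by a closing bracket. Hospitalization is an inclusion criterion (section 4.1), so the variable applies to everyone enrolled. It is absent from the numbered endpoint lists in sections 1.1 and 1.2. The nearest numbered endpoint is secondary endpoint 5, "hospital-free days through day 28". The hypothesis in section 1.1 expects that adding the drug to "standard care will reduce need for ventilation, length of mechanical ventilation, hospital length of stay, ICU length of stay and improve survival".

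The analysis text in section 6.1, which repeats section 1.5, names two models. The first is "We will analyze continuous measures by means of linear regression and present as mean differences". The second is "For binary outcomes, we will present data as risk ratios from a binomial regression model". Intention-to-treat is stated in these terms: "For primary efficacy, we will do an intention-to-treat analysis and include all patients who have undergone randomization".

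On follow-up, section 1.2 says "Data collection will end after 28 days, or the patient dies or withdraws consent". Deaths are expected, because secondary endpoint 1 is "all-cause mortality assessed on day 15 and day 28". Neither section gives a time-to-event method, a censoring rule, a competing-event rule, or a discharge time for a patient who dies or is still an inpatient at day 28. The rest of the document does not supply one either.

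**The concern.** A time to discharge alive exists only for patients who leave hospital alive within the 28 days. A patient who dies never has one, and for a day-28 inpatient it is known only to exceed 28 days. Linear regression needs a number for every patient it includes. With no rule supplied, software drops the patients without one. What remains is a comparison of discharged patients, and the treatment may itself change who belongs to that group.

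The direction of the error matters. If the drug saves some very sick patients and they go home late, they enter the treated arm's average with long times, while their counterparts in the control arm are missing because they died. The treated mean rises although nobody did worse. The reverse also holds: a drug that killed patients who would have gone home late would lower its own mean. Improved survival is part of the trial's hypothesis, so the first situation is one the trial hopes to see.

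**Working it through.** **The plan's own figure.** Section 1.5 gives 66 per arm for 90% power, two-sided 0.05, a 20% difference on a mean of 4.5, SD 1.6. The difference is 0.2 × 4.5 = 0.9 points. Then n per arm = 2 × 1.6² × (1.960 + 1.282)² / 0.9² = 66.4, or 67 rounded up; power at 66 is 89.8%. The figure reproduces. It concerns the primary endpoint, and nothing below changes it.

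**Mechanism by hand.** All rates here are assumed. Control arm, 66 patients: 46 discharged at a mean of day 8, 13 deaths, 7 still in hospital at day 28. The drug changes one thing only: k patients who would have died are discharged at day 22.

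- Mean among the discharged, control: 8.00 days.
- Mean among the discharged, drug: (46 × 8 + k × 22) / (46 + k).
- Mean over all 66 with everyone undischarged set to 28 days, control: (46 × 8 + 20 × 28) / 66 = 14.06.
- The same, drug: (46 × 8 + k × 22 + (20 − k) × 28) / 66.

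| k | Drug mean, discharged only | Difference | Drug mean, all 66, undischarged = 28 | Difference | Discharged by day 28 (control 46/66) |
|---|---|---|---|---|---|
| 3 | 434/49 = 8.86 | +0.86 | 910/66 = 13.79 | −0.27 | 49/66 |
| 6 | 500/52 = 9.62 | +1.62 | 892/66 = 13.52 | −0.55 | 52/66 |
| 9 | 566/55 = 10.29 | +2.29 | 874/66 = 13.24 | −0.82 | 55/66 |

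The same patients give opposite signs depending on a rule that the plan does not state. Exchanging the arms gives the mirror case: a harmful drug looks faster by the same amounts.

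**Size by simulation.** 66 per arm, 4,000 trials per scenario, t test among patients discharged by day 28 (the same as linear regression on arm alone). Assumed: non-critical patients have a median of 7 days to discharge, lognormal with log-SD 0.6. Critical patients die in the control arm, and rescued ones are discharged at about day 20.

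| Deaths in controls | Share rescued by drug | Other effect | Mean difference (days) | Significant in the wrong direction |
|---|---|---|---|---|
| Null | none | none | about 0 | 2.2% |
| 10% | 1/3 | none | +0.43 | 6.5% |
| 15% | 1/5 | none | +0.42 | 6.7% |
| 15% | 1/3 | none | +0.65 | 9.6% |
| 15% | 2/3 | none | +1.27 | 23.6% |
| 20% | 1/2 | none | +1.30 | 24.2% |
| 15% | 1/3 | 10% faster discharge in the others | −0.03 | 2.1% |

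With deaths and day-28 inpatients set to 28 days, the 15% scenarios favour the drug by about 0.8 days (two thirds rescued) and 0.4 days (one third rescued). Wrong-direction significance is then about 1%.

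A simulation close to the hand example (early discharges with mean 8 days, rescued patients discharged on days 16 to 28) gives about 14%, 34% and 54% for k = 3, 6 and 9. That example assumes 13/66 = 20% mortality and later discharge of the rescued. It shows how strongly the result depends on the inputs and is not used as the estimate of size.

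**The case against.** Four points on the other side carry weight.

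- **The discharged-only analysis is inferred.** A reader might take section 6.1 to prescribe a regression restricted to discharged patients. It does not: it speaks of continuous measures, does not name time to discharge, and restricts nothing. What stands is that the only other model is for binary outcomes and that no rule assigns a value to the rest. Dropping them is therefore the most direct reading, but not the only one.
- **The variable is outside the endpoint lists.** It appears in a loose list with compliance and vital signs. Hospital-free days is the formal discharge endpoint, the ordinal scale at days 15 and 28 holds discharge and death together, and mortality is reported alongside. A large rescue from death would not be judged on discharge times alone. This lowers the severity. It does not supply the missing rule, and the value of hospital-free days for a patient who dies is also undefined.
- **The largest figures need favourable inputs.** The 24% results require mortality to fall from 15% to 5%, or from 20% to 10%, with late discharge of the rescued and no benefit to anyone else. The protocol itself hopes for shorter stays, and a 10% speed-up in the other patients removes the effect in the scenario tested.
- **Intention-to-treat is not broken here.** A reader might infer that a promised intention-to-treat comparison is lost. The plan makes that promise for primary efficacy only.

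**Conclusion.** The point holds as a gap with a predictable direction of bias. Time to discharge is a named outcome measure, the only method that could cover it is a regression of means, and patients who die or remain in hospital have no defined value. If the regression is run on observed discharge times, it conditions on an outcome that arises after randomization, and a life-saving drug can appear to delay discharge.

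Under the assumed rates the spurious delay is about 0.4 to 1.3 days, with wrong-direction significance in about 6% to 24% of trials against roughly 2.5% by chance. Only the mechanism and its direction follow from the plan; the size rests on assumptions. The effect vanishes with a modest benefit in other patients, or if deaths and undischarged patients are set to 28 days.

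The documents do not support the stronger reading that the sign will be wrong, or that a numbered endpoint is compromised. The primary analysis and sample size are untouched. Severity is minor to moderate.

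**What to change.** Add to section 6.1:

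> Time to discharge alive will be analysed in all randomized patients through day 28 as a time-to-event outcome with death as a competing event, reporting cumulative incidence by arm and a subdistribution hazard ratio. Patients in hospital at day 28 will be censored then, and patients who withdraw consent before discharge will be censored at withdrawal. This outcome will not be analysed by linear regression among discharged patients.

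Where the only censoring is at day 28, this is equivalent to keeping deaths in the risk set as never discharged through day 28, which is simple to program.

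The cost is a few lines of analysis text, with no change to sample size or conduct. Section 1.2 says that case report form Module 3 is completed at discharge or death, so the dates are very likely captured already. The form itself is not in the text reviewed, so this should be confirmed. The small downside is that the result is a hazard ratio or a cumulative incidence, not a mean difference in days.

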6.2 Data Security

- 1. The Human Research Oversight Committee (HROC) is responsible for oversight of protocol progress, conduct, and compliance. The Rutgers Cancer Institute of New Jersey's Data Safety Monitoring Plan (DSMP) activities fall under the purview of HROC. In order to ensure the execution of the protocol with a minimum number of obstacles, the HROC focuses on the following objectives:
 - Monitor data and safety of CINJ investigator-initiated trials, including serious adverse events (SAE), enrollment progress, stopping rules, etc.
 - Review the safety of all trials conducted at CINJ.

Protocol Title: ATTAC-19 - Aggrenox To Treat Acute Covid-19 Pro#2020001469

Protocol Version 6 Date: 4/18/2021

7/21/2021

Rutgers, The State University of New Jersey [name]

- Review enrollment to cooperative group and industry-sponsored studies.
- Review study compliance through deviation reports of all trials, Quality Assurance (QA) audit reports of CINJ investigator-initiated trials and external monitoring reports of all trials.
- Conduct response review for investigator-initiated trials.

6.3 Data and Safety Monitoring

A. Data/Safety Monitoring Plan

The Principal Investigators will be responsible for monitoring the data, assuring protocol compliance, and conducting the safety reviews at the specified frequency, which must be conducted at a minimum of once a month (including when re-approval of the protocol is sought). The Rutgers Cancer Institute of New Jersey's Human Research Oversight Committee (HROC) will be the DSMB of record. During the review process, the principal investigators (serving as monitor) will evaluate whether the study should continue unchanged, require modification/amendment, or close to enrollment. Either principal investigator, IRB or either Data or Safety Monitoring Committee have the authority to stop or suspend the study or require modifications at each institution. The PIs will be responsible for sharing this information in a timely fashion and coordinating appropriate parallel actions at the other institution.

An audit will be conducted following enrollment of the first two (2) or three (3) patients. Subsequent audits will occur dependent on the rate of enrollment. More frequent audits of patient data and study conduct will occur if necessary. Prior audit findings and/or situations that may arise during the study will determine the need for more frequent auditing. All audit findings will be discussed with the principal investigator and the Rutgers University IRB.

B. Data/Safety Monitoring Board Details

The Human Research Oversight Committee (HROC) is responsible for oversight of protocol progress, conduct, and compliance. The Rutgers Cancer Institute of New Jersey's Data Safety Monitoring Plan (DSMP) activities fall under the purview of HROC. In order to ensure the execution of the protocol with a minimum number of obstacles, the HROC focuses on the following objectives:

- Monitor data and safety of CINJ investigator-initiated trials, including serious adverse events (SAE), enrollment progress, stopping rules, etc.
- Review the safety of all trials conducted at CINJ.
- Review enrollment to cooperative group and industry-sponsored studies.
- Review study compliance through deviation reports of all trials, Quality Assurance (QA) audit reports of CINJ investigator-initiated trials and external monitoring reports of all trials.
- Conduct response review for investigator-initiated trials.

6.4 Reporting Results

A. Individual Subjects' Results

Protocol Title: ATTAC-19 – Aggrenox To Treat Acute Covid-19 Pro#2020001469

Rutgers, The State University of New Jersey [name]

Results of individual patient assessments will be shared with the individual patient as these are part of the medical record and impact medical care. These results are part of routine care (safety labs, routine radiology procedures, and physical examinations).

B. Aggregate Results

Aggregate research results will not be shared with the study participants.

C. Professional Reporting

The policies and procedures of Rutgers University's legal department (see: Investigator's Handbook) will govern publication of the trial. It is expected that the results of this trial will be submitted for publication in a timely manner following the conclusion. The PI and all co-authors prior to submission or use must review any abstract or manuscript.

D. Clinical Trials Registration, Results Reporting and Consent Posting

ClinicalTrials.Gov Registration and Data Reporting: Under the terms of the Food and Drug Administration Modernization Act (FDAMA) and the Food and Drug Administration Amendments Act (FDAA), the Sponsor of the trial is solely responsible for determining whether the trial and its results are subject to the requirements for submission to the Clinical Trials Data Bank, http://www.clinicaltrials.gov. Information posted will allow subjects to identify potentially appropriate trials for their disease conditions and pursue participation by calling a central contact number for further information on appropriate trial locations and trial site contact information.

This is a research study which prospectively assigns human participants to health related interventions. The study has been registered on clinicaltrials.gov per FDA Regulations and will be updated at least every 6 months.

